4.3.3 Qualifications for Participation in Part B (Therapy at 1 and/or 3 mg/kg)

Subjects are eligible for continued SBC-103 dosing in Part B if they do not meet any Exclusion criteria listed above and if they meet the following:

- 1. Completion of Part A with no unmanageable study drug toxicity;
- 2. Continue to meet Section 4.3.1 Inclusion Criteria items 4-7; and

3. SRC and Sponsor have reviewed the subject's safety data from Part A and have deemed it acceptable for the subject to re-initiate dosing in Part B.

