4.3.4 Qualifications for Participation in Part C (Therapy at 5 and/or 10 mg/kg)

Subjects are eligible for continued SBC-103 dosing at a higher dose (5 or 10 mg/kg QOW) in Part C if they do not meet any Exclusion criteria listed above and if they:

- 1. Have completed at least 4 doses of 3 mg/kg in either Part A or Part B with no unmanageable study drug toxicity; and
- 2. Continue to meet Section 4.3.1 Inclusion Criteria items 4-7.

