5.1.2 Subject Eligibility

All subjects will be assessed for eligibility against the inclusion and exclusion criteria described in Section 4.3. All eligibility assessments are to be completed prior to the commencement of any Day 0 procedure (ie, any invasive procedures, including general anesthesia or sedation, lumbar puncture and MRI). Sites are requested to provide documentation/confirmation of eligibility to the Sponsor, which is subject to Sponsor review and agreement.

In Part B, all subjects will also be assessed to determine whether they qualify for re-initiation of SBC-103 dosing as described in Section 4.3.3, and subjects will be permitted to enter Part C (expanded dose escalation) if they meet the criteria in Section 4.3.4.

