6 STUDY TREATMENTS

6.1 Treatments Administered

Part A (Initial Therapy)

In Part A, all subjects in each dosing cohort (0.3 mg/kg, 1 mg/kg, 3 mg/kg) will receive SBC-103 administered by IV infusion QOW for 24 consecutive weeks. Infusions must be administered at least 10 days apart. All study visits will be scheduled relative to Day 0.

Part B (Therapy at 1 and/or 3 mg/kg)

For eligible subjects, dosing in Part B may not be re-initiated sooner than 4 weeks and no greater than 4 weeks and 3 days after the last dose administered in Part A (See SOA). Subjects who received doses of either 0.3 mg/kg or 1 mg/kg during Part A may escalate to the next higher dose of SBC-103 considered to be safe by the Sponsor and SRC with their first dose in Part B or at any time thereafter. Subjects who received doses of 0.3 mg/kg in Part A may be considered for a second dose escalation to 3 mg/kg at any time during Part B provided that they have tolerated at least 2 doses of 1 mg/kg in Part B (see Section 3.1.2).

In Part B, if a subject misses ≥ 3 consecutive infusions, additional assessments will be required prior to resuming dosing, including safety labs (hematology, chemistry, coagulation, urinalysis and pregnancy test, where applicable), and serum and urine HS. If ≥ 6 consecutive infusions are missed, additional assessments, including lumbar puncture for CSF collection, may be required prior to resuming dosing as determined by the Sponsor in consultation with the investigator. The next scheduled lumbar puncture would not be necessary if ≤ 2 months have elapsed since the previous lumbar puncture.

Part C (Therapy at 5 and/or 10 mg/kg)

Dosing in Part C may start as soon as a subject is eligible (Section 4.3.4) and according to the schema outlined in Section 3.1.3. Therefore, each subject's duration of treatment and assessments in Part B may vary. Once a patient is dose escalated in Part C, the study visit schedule is reset to Day 0 Part C (Day 0C). In Part C, subjects will be randomized such that at least 1 subject from each cohort assigned in Part A will receive SBC-103 at 5 mg/kg and at least 1 subject from each cohort assigned in Part A will receive SBC-103 at 10 mg/kg. Thus each of the assigned dose levels from Part A will be represented in each of the 2 dose levels being studied in Part C. Infusions must be administered at least 10 days apart. All study visits in Part C will be scheduled relative to Day 0C.

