6.2 Stopping Rules

6.2.1 Stopping Rules in Individual Subjects

During Part A (Initial Therapy), Part B (Therapy at 1 and/or 3 mg/kg), and Part C (Therapy at 5 and/or 10 mg/kg), subjects who experience a severe IAR, a serious or severe AE that is

Page 75 of 121

considered related to SBC-103, or a significant elevation in specific laboratory values will have SBC-103 dosing paused based on the rules described below.

For IARs:

- Subjects who develop a severe IAR, as defined in Section 7.1.3, must stop treatment until their information is reviewed by the SRC. Dosing with alterations to the infusion regimen (eg, pretreatment or slowing the rate of infusion) may resume once the SRC and the Sponsor approve.
- Subjects with mild or moderate IARs can continue receiving SBC-103 in the study. The SRC or Sponsor may recommend alterations to the infusion regimen (eg, pretreatment or slowing the rate of infusion).

For all other AEs (ie, AEs that are not characterized as IARs):

- Any event considered related to SBC-103 which is either serious or severe will result in pausing additional dosing in an individual subject. The SRC and the Sponsor will review the data and will resume dosing only after review and agreement.
- Subjects with mild or moderate non-serious AEs can continue receiving SBC-103 in the study.

For Laboratory Values:

- Dosing will be paused based on confirmed elevations in AST or ALT under the following circumstances:
 - In the event that a subject's AST or ALT is greater than or equal to 2 times the ULN (when baseline ALT or AST was within normal limits)
 - In the event that a subject's AST or ALT is greater than or equal to 3 times the ULN (if baseline ALT or AST greater than 1.5 ULN).

Dosing will only resume after AST or ALT have returned to baseline or to study nadir (nadir values may be confirmed by additional lab sampling at the discretion of the investigator, using the same lab for analysis of each sample), or normalized if the baseline level was within normal limits.

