The subject should be restarted at a reduced dose. For example, if a subject was receiving a dose of 10 mg/kg, he/she would be restarted at 5 mg/kg; subjects receiving 5 mg/kg would be restarted at 3 mg/kg; etc. In the event that the subject was receiving a dose of 0.3mg/kg, he/she may resume at the 0.3 mg/kg dose only after AST or ALT have returned at least to baseline or to study nadir (nadir values may be confirmed by additional lab sampling at the discretion of the investigator, using the same lab for analysis of each sample), or normalized if the baseline level was within normal limits.

If after resuming treatment at the lower dose, the ALT or AST elevation recurs at greater than or equal to 2 times the ULN (for those with ALT or AST within normal limits at baseline) or 2 times the baseline value (for those with abnormal ALT or AST at baseline) study drug should be stopped and not resumed. Dosing will be paused based on confirmed elevations in AST or ALT with accompanying elevations in the following

• Confirmed bilirubin greater than 1.5 times ULN

- Confirmed INR increase of 0.2
- Eosinophilia (more than 5%), rash or fever

If these bilirubin and INR values normalize (and the independent SRC believes that it is safe to do so), the subject may resume dosing on a lower dose of the study drug (eg, those on a 3 mg/kg would resume dosing at 1 mg/kg, those on a 0.3 mg/kg dose would resume the 0.3 mg/kg dose). However, in this scenario, if a subject develops recurrent elevations in AST or ALT (with or without elevations in total bilirubin or INR), the drug should be stopped and not resumed.

Subjects whose rise in LFTs is accompanied by eosinophilia (more than 5%), rash or fever should not be restarted on the study drug.

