The SRC will perform a review of each subject's available safety data prior to the start of Part B for each subject. The SRC will also conduct periodic reviews (at least every 6 months during the first year and annually thereafter) of aggregate safety data as indicated in the SRC Charter.

Ad-hoc reviews of safety data will be performed on an as-needed basis in the event of emerging safety signals of clinical concern in one or more subjects, including subjects who meet the predefined stopping rules for study treatment (see Section 6.2). Additionally the Sponsor will review the PD/efficacy every 6 months during the first year and at least annually thereafter to confirm the appropriateness of continued dosing.

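### Part C entry (Protocol 4.3.4) does not require SRC review of a child who was dose-reduced for an isolated ALT/AST rise after four 3 mg/kg doses and then recovered

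*Protocol*

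**What the plan says.** Protocol 4.3.3 (Part B) has three items. The third requires that the SRC and Sponsor have reviewed the child's Part A safety data and "have deemed it acceptable for the subject to re-initiate dosing in Part B". Section 7.5 repeats that individual SRC review for Part B.

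Protocol 4.3.4 (Part C) has two items besides the exclusion criteria: the dose count, "Have completed at least 4 doses of 3 mg/kg in either Part A or Part B with no unmanageable study drug toxicity", and continued compliance with inclusion items 4 to 7. No review item follows. Section 5.1.2 states that "subjects will be permitted to enter Part C (expanded dose escalation) if they meet the criteria in Section 4.3.4", and 6.1 lets dosing begin once 4.3.4 is met, subject to the schema in 3.1.3.

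Protocol 6.2.1 pauses dosing for a confirmed ALT or AST rise. For a rise without other findings, "Dosing will only resume after AST or ALT have returned to baseline or to study nadir" (or normalised, if baseline was normal), and then "The subject should be restarted at a reduced dose". From 3 mg/kg the next level down is 1 mg/kg. Nothing in 6.2.1 says whether such a child may later be escalated again.

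**The concern.** A 6.2.1 reduction is a safety action. Part C entry is the point at which the dose goes above the level at which the liver signal appeared. For that step the protocol asks for less individual review than it asks for re-starting treatment in Part B, although the doses are higher. If the rise was dose-related, the child meets a larger dose with no required decision that this is acceptable for that child. After entry, most children have no scheduled chemistry until two doses at the new level have been given.

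**Working it through.** **1. Which 6.2.1 events reach the SRC before restart**

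| Event | What restart requires |
|---|---|
| Severe infusion reaction | SRC and Sponsor approval |
| Other related serious or severe AE | SRC and Sponsor review and agreement |
| ALT/AST with bilirubin or INR rise | Normal values and the SRC's view that it is safe; lower dose |
| ALT/AST with eosinophilia, rash or fever | None: "Subjects whose rise in LFTs is accompanied by eosinophilia (more than 5%), rash or fever should not be restarted on the study drug" |
| ALT/AST alone | Laboratory recovery; lower dose; no SRC step named |

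The gap is the last row, for an event not rated serious or severe. Such a child can pass both the restart and Part C entry without a mandatory individual SRC review.

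**2. The SRC decisions within Part C (3.1.3.1).** Expansion at each level rests on 24-hour data from the first child at that level. The step to 10 mg/kg rests on one child with two doses at 5 mg/kg, plus data from others already at 5 mg/kg. None of these looks at the entering child's own history.

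**3. Size of the dose step from 3 mg/kg.** 5/3 = 1.67; 10/3 = 3.33.

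**4. When the gap can open.** SAP Section 4 gives 90 to 110 weeks in Part C up to Week 156. Entry is therefore between 156 − 110 = Week 46 and 156 − 90 = Week 66. Part B chemistry after Week 28 (Appendices B and C) is at Weeks 36, 44, 52 and 60, then 68. I count draws after Week 28 because Part A data are covered by the Part B entry review, and I assume visits every two weeks on schedule.

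- Cohort 3 reached four doses at 3 mg/kg in Part A.
- Cohort 2, if raised at Week 28, has doses at Weeks 28, 30, 32 and 34, so the Week 36 pre-dose draw follows the fourth dose.
- Cohort 1 had at least 5 doses at 1 mg/kg in Part B (Section 1.4.1), at Weeks 28 to 36. Its earliest 3 mg/kg doses are Weeks 38, 40, 42 and 44. The Week 44 draw is pre-dose, so the first draw after four doses is Week 52.

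| Entry | Cohorts 2 and 3 | Cohort 1 |
|---|---|---|
| Week 46 | Week 36 (Week 44 is too late) | none |
| Week 66 | Weeks 36, 44, 52, 60 | Weeks 52, 60 |

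Week 44 is set aside for a Week 46 entry because 46 − 44 = 2 weeks. Section 5.2.1 allows confirmation as late as the next scheduled visit, which is Week 46, so pause, recovery and restart could hardly fit. The Week 60 draw leaves 66 − 60 = 6 weeks. Unscheduled tests could add draws.

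**5. Aggregate SRC review.** If the six-monthly review in 7.5 is counted from Week 28 (the start is not stated), it falls due by 28 + 26 = Week 54. That is after the earliest entries and concerns aggregate data.

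**6. After entry.** Doses fall at Day 0C and Week 2C. The first scheduled post-dose chemistry is pre-dose at Week 4C, hence after two doses. The exception is the first child at each level, who has a Day 1C draw (Appendix D).

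**The case against.** The strongest reply is that such a child would not go unseen.

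- Section 7.5 names children who meet a 6.2 stopping rule as subjects for ad hoc SRC review, and gives the SRC the task of advising on escalation.
- Section 7.2.4 sends possible drug-induced liver injury to a hepatologist.
- The synopsis lets the SRC or Sponsor request a pause in one child.
- Exclusion 8 brings in Investigator and Sponsor judgement, and 5.1.2 makes eligibility subject to Sponsor agreement.
- Section 3.1.2 has Part B dose changes considered by the Sponsor with the SRC. It offers Part C only to children who tolerated four doses at 3 mg/kg, who may then be considered.
- Appendix D has an eligibility check and pre-dose chemistry at Day 0C.
- Section 3.3.3 gives a reason for light gating: by then every enrolled child had prior exposure and safety data.

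Much of this stands, and it rules out the reading that nobody would look at the child or that the Sponsor has no role. It does not supply the missing condition. Ad hoc review is as-needed and has no stated link to the first Part C dose. The 5.1.2 agreement sits in the Day 0 paragraph, so its reach to Part C is unclear. Exclusion 8 and the Day 0C chemistry would catch a current elevation but not a recovered one. The 6.2.1 reduction is prescribed by rule, so it need not pass through the 3.1.2 consultation. A child may have tolerated four doses and had the rise later; 3.1.2 does not say who then decides. Section 3.3.3 does not address a child with a 6.2.1 event.

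A reader might also put the step at 5- or 10-fold, measured from 1 mg/kg. That overstates it: the child has already had at least four doses at 3 mg/kg, so 1.7 and 3.3 are the relevant ratios.

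**Conclusion.** The point holds for a narrow case: an isolated ALT/AST rise, not rated serious or severe, after four doses at 3 mg/kg, with pause, reduction and recovery and without recurrence. (Recurrence after restart at the lower dose stops treatment for good.) The written entry rule admits that child to 1.7 or 3.3 times the dose of the event, and no SRC review is a condition of entry.

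A reader might infer that children were in fact escalated unsafely, or that the protocol authorises escalation after a liver signal. The documents support neither. The number affected is not in the available text and may be zero, and the protocol is silent on re-escalation. The SRC Charter is not among the documents and may contain such a check. The week counts assume on-schedule visits and the SAP's range for time in Part C. Since the SAP records that development stopped in July 2017, this is a judgement on the plan as written. It is a cheap improvement that should be made; confidence is medium.

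**What to change.** Add an item 3 to 4.3.4, with matching synopsis text, along these lines: *for any subject previously paused or dose-reduced under Section 6.2.1, the SRC and Sponsor have examined that subject's safety data from Parts A and B and have judged it acceptable to start Part C dosing.* Item 3 of 4.3.3 is the model but cannot be copied as it stands, because it refers to Part A data and Part B dosing. Add a matching sentence to 7.5, so that the stopping-rule review already named there is tied to the first Part C dose.

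The cost is one SRC agenda item and a possible short delay for each affected child, and nothing for the others. The clinical decision stays with the SRC and Sponsor.

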4.4 Concomitant Medications and Treatments

Concomitant medications include prescription and over-the-counter medications, prophylactic and therapeutic vaccines, herbal medications, vitamins, and dietary/nutritional supplements, as well as any investigational medications the subject may have received. Concomitant treatments include diagnostic, palliative, or interventional procedures (eg, hematopoietic stem cell transplant, bone marrow transplant).

At the Screening visit, information on all medications and treatments received by the subject within the preceding 4 weeks will be recorded in the case report form (CRF). Thereafter, reasonable efforts will be made to ascertain all changes in concomitant medications and treatments from Screening until the subject completes the safety follow-up phone call. Particular attention will be given to any changes in the dose or dosing regimen of genistein or melatonin, antihistamines, chloral hydrate, benzodiazepines, thioridazine, carbamazepine, and sodium valproate. Note that subjects who are on a stable dosing regimen for any of the listed medications at the time of Screening, including a low dose of genistein ($\leq 150 \text{ mg/kg/day}$), should remain on the dosing regimen during the study. Dose adjustments or discontinuation of these medications should occur only when there is a clear medical reason and should be pre-approved by the Sponsor. Information on all concomitant medications and treatments will be recorded in the CRF and will include the name of the medication (brand or generic) or therapy, reason for use, start date, stop date, dose, route of administration (if applicable), and frequency of administration.

4.5 Discontinuation of Subjects

4.5.1 Premature Withdrawal from Study Participation

Subjects have the right to withdraw from the study at any time for any reason, without prejudice to further treatment.

The Investigator and Sponsor also have the right to withdraw subjects from the study at any time. Specific reasons for discontinuation may include, but are not restricted to, the following:

- Intercurrent illness
- Adverse events, including severe infusion reactions
- Pregnancy
- Protocol deviation or non-compliance
- Termination of the study by the Sponsor

4.5.2 Procedures for Discontinuation

If a subject discontinues at any time after being dosed with SBC-103 (excluding ineligibility for Part B), all efforts should be made to have the subject complete follow-up visit procedures, including End of Study/Early Withdrawal Visit per SOA (refer to Section 14). All subjects who withdraw should be asked about the reason(s) for their discontinuation and about the presence of AEs. The date and the reason for discontinuation will be recorded.

When a subject fails to return for scheduled assessments, the following efforts should be made to contact him/her (this would generally apply to the parent/caregiver) to determine a reason for the failure to return: three phone attempts, including the date and time, to be documented in the subject's chart. If there is no response to the telephone calls, a certified letter should be sent. After these efforts have been exhausted, a subject should be identified as lost to follow-up.

4.6 Subject Replacement Policy

Subjects who discontinue prior to administration of SBC-103 will be replaced. Subjects who discontinue for reasons other than medically important adverse event(s) considered related to the administration of SBC-103 may be replaced after discussion between the Sponsor and the SRC.

4.7 Subject Re-screening

Subjects who were unable to complete all Screening procedures within the 28-day screening window may be re-screened. The subject will be re-consented and screening procedures will be repeated at the discretion of the Investigator after discussion with the Medical Monitor.

5 STUDY PROCEDURES

5.1 Study Assessments

A Schedule of Study Assessments (SOA) is presented in Section 14.1 (Appendix A) for Part A (Initial Therapy), in Sections 14.2 and 14.3 (Appendices B and C) for Part B (Therapy at 1 and/or 3 mg/kg), and in Section 14.4 (Appendix D) for Part C (Therapy at 5 and/or 10 mg/kg). Unless otherwise specified, all study assessments described in the following sections are applicable to Parts A, B, and C of this study. The SOA provides detailed information regarding the time points for all of these assessments.

5.1.1 Informed Consent/Assent

The subject (or the subject's parent or legal guardian) will be given a consent form as well as a verbal explanation of the study, including information about the study procedures, and will have all questions adequately addressed. The subject (or the subject's parent or legal guardian) must sign and date a consent form that has been approved by the appropriate IRB/IEC before screening procedures are initiated, and will be given a copy of the signed and dated informed consent form. In addition, age and comprehension-appropriate assent will be obtained from subjects below the age of consent, as required by local regulations.

5.1.2 Subject Eligibility

All subjects will be assessed for eligibility against the inclusion and exclusion criteria described in Section 4.3. All eligibility assessments are to be completed prior to the commencement of any Day 0 procedure (ie, any invasive procedures, including general anesthesia or sedation, lumbar puncture and MRI). Sites are requested to provide documentation/confirmation of eligibility to the Sponsor, which is subject to Sponsor review and agreement.

In Part B, all subjects will also be assessed to determine whether they qualify for re-initiation of SBC-103 dosing as described in Section 4.3.3, and subjects will be permitted to enter Part C (expanded dose escalation) if they meet the criteria in Section 4.3.4.

5.1.3 Medical History

A complete medical history will be obtained for each subject at Screening, including (but not limited to) the following:

- Historical results of NAGLU enzyme activity testing and genetic mutation analysis, as applicable;
- Presence (and date of onset, if known) of the following clinical manifestations or disorders as applicable:
 - Cognitive delay/difficulties
 - Abnormal facial features (flat nasal bridge, enlarged lips, enlarged mouth and tongue, abnormal thickening/darkening/coarseness of eyebrows)
 - Hepatomegaly
 - o Language delay/difficulties, or regression of language skills
 - Abnormal behaviors (hyperactivity, aggressiveness, irritability, endangering behaviors)
 - Autism spectrum disorder

Page 60 of 121

- Epilepsy
- Motor function delay/difficulties, including loss of independent walking
- Sleep disturbances (settling difficulties, early awakening, complete reversal of day-night rhythm, obstructive sleep apnea)
- Ear-nose-throat problems (recurrent ear infections, adenoidectomy or tonsillectomy, grommets, documented history of hearing loss)

In addition, a family medical history will be obtained, documenting the number of siblings and the medical status of each sibling, including the presence of abnormalities suggestive of MPS IIIB. Where NAGLU enzyme activity or genetic testing has confirmed the presence of MPS IIIB in additional family members, data will be collected on relationship, age of diagnosis, medical complications, and, if applicable, cause of death.

Refer to Section 4.4 for details on collection of medication history and concomitant medications/treatments.

